6.6.4 Reporting Serious Adverse Events

All SAEs will be collected from the time of informed consent until 30 days after the last study treatment and regardless of study drug relationship, must be reported by facsimile to the CRO within 24 hours of knowledge of the event. The facsimile report should include all available information requested on the SAE form (refer to Key Study Personnel page for fax number to report SAEs). The SAE form will collect data surrounding the event, e.g., the nature of the symptom(s), time of onset in relation to initiation of therapy, duration, intensity, and whether or not therapy was interrupted or discontinued. The Investigator's assessment of the probable cause of the event will also be included. In addition, relevant medical history, concomitant medications, laboratory and diagnostic reports, and procedures, as well as all pertinent medical information

related to the event, will also be collected.

The CRO will forward SAE queries directly to the site requesting incomplete or missing information. It is the Investigator's responsibility to be diligent in providing this information back to the CRO as soon as it is available. Initial reports of SAEs should not be left on telephone voicemails. Always fax SAE reports and follow-up with a telephone call if needed.

All sites will follow their institutional requirements for submission of SAEs to their IRB.

6.6.4.1 Expected Adverse Events

Myelosuppression and its associated complications due to underlying leukemia and/or intensive anti-leukemia therapy are expected events during therapy for AML.

Hospitalization or prolongation of hospitalization for the treatment of the following events that are known to be associated with myelosuppression from leukemia and/or intensive leukemia therapy, are also considered to be expected. These events still need to be recorded as AEs on the eCRF:

- Fatigue, weakness and/or shortness of breath associated with anemia
- Febrile neutropenia
- Bleeding due to thrombocytopenia e.g., epistaxis, gastrointestinal bleeding
- Bacteremia, sepsis, or other infections
- Neutropenic colitis.

Death due to progression of AML and/or its associated complications are expected in the patient population and are listed in Appendix E. Deaths should be reported with Investigator's assessment of causality.

Appendix E also contains a list of known/expected AEs for cytarabine and idarubicin. The IB contains expected events known for CX-01 (63).

6.6.4.2 Investigator's Notification of the Sponsor

All Investigators will be thoroughly instructed and trained on all relevant aspects of the Investigator's reporting obligations for SAEs. This information, including all relevant contact details, is summarized in the Investigator site file. This information will be updated as needed. Serious AEs occurring during the study must immediately (within 24 hours of Investigator's awareness) be reported per Section 6.6.4 to the recipient detailed in the manual.

Serious AEs occurring after the protocol-defined observation period will be processed by

the Sponsor according to all applicable regulations.

6.6.4.3 *Notification to the Independent Review Board*

Notification to the IRB about all relevant events (e.g., SAEs, SUSARs) will be performed by the Sponsor or Sponsor's designee and/or by the Investigator according to all applicable rules/regulations.

6.6.4.4 *Notification to the Authorities*

The processing and reporting of all relevant events (e.g., SAEs, SUSARs) to the authorities will be done by the Sponsor or Sponsor's designee and/or by the Investigator according to all applicable rules/regulations.

6.6.4.5 *Sponsor's Notification to the Investigational Site*

The Sponsor or designee will inform all investigational sites about reported relevant events (e.g., SUSARs) according to all applicable regulations. The Sponsor or Sponsor's designee will send SUSARs to a site once the site initiation visit has occurred and will stop sending SUSARs to a site once the last subject End of Treatment Visit for that site (30 days after last dose) occurs.

6.6.5 Data and Safety Monitoring Committee

A DSMC will serve as a monitoring advisory group for the study. The primary role for the DSMC will be to examine the safety and efficacy throughout the duration of the study.

The DSMC will be created to further protect the rights, safety, and well-being of patients who will be participating in the study by monitoring their progress and their results. The DSMC comprises qualified scientists, who are not Investigators in the study and not otherwise directly associated with the Sponsor. The DSMC will be described in detail in the DSMC Charter.

The DSMC will monitor data during the study. All activities of the DSMC will be documented. This documentation will contain data summaries and analyses provided to the committee as well as minutes of any ad-hoc meetings, as necessary.

6.6.6 Pharmacokinetics

Steady-state PK samples will be collected at selected sites only. Pharmacokinetic samples will be collected during the induction cycle on Days 3 and 5.

The first 6 patients assigned to a CX-01 dose level (low; 0.125 mg/kg/hour, intermediate; 0.25 mg/kg/hour, and high doses; 0.325 mg/kg/hour) will have PK's drawn (consistent with the original protocol which included 4 dose groups).

The same 6 patients that participate in Day 3 PK sampling will have one additional blood sample drawn on Day 5 of treatment. The PK samples may be drawn before the CX-01 infusion is stopped to change the CX-01 bag and tubing. All PK blood samples must be drawn from the opposite arm to the CX-01 IV infusion.

The site will document actual dates and times of sample collection in the source documents and eCRF. Any reason for missed or lost samples should be recorded.

Pharmacokinetic blood samples will be processed and may be batch shipped for analysis to a bioanalytical laboratory. Full details of sample handling and shipment can be found in the Study Operations Manual (also refer to Appendix F for details).

6.7 Data Quality Assurance

The Sponsor or Sponsor's designee performs quality control and assurance checks on all clinical studies that it conducts. Before enrolling any patients in this study, the Sponsor or Sponsor's designee and the Investigator will review the protocol, the IB, the eCRFs and instructions for their completion, the procedure for obtaining informed consent, and the procedure for reporting AEs and SAEs. The Sponsor's designee will monitor the conduct of the study at the site and will verify eCRFs against source documents. Additionally, the Sponsor's designee will use automated validation programs to help identify missing data, selected protocol deviations, out-of-range data, and other data inconsistencies. Requests for data clarification or correction will be electronically provided to the Investigator for resolution.

In accordance with ICH GCP and the Sponsor's audit plans, this study may be selected for audit by representatives from the Sponsor or Sponsor's designee. Inspection of site facilities (e.g., pharmacy drug storage areas, laboratories, etc.) and review of study-related records will occur to evaluate the study conduct and compliance with the protocol, ICH GCP, and applicable regulatory requirements.

6.8 Statistical Methods

6.8.1 Determination of Sample Size

A total of 25 evaluable patients per arm will provide 71.8% power for each test comparing a dose with control via a Fisher's exact test at 1-sided $\alpha = 0.15$ to detect a difference between a control proportion 0.55 and an experimental dose proportion 0.80; these tests will be conducted in a fixed sequence: higher dose versus control first and lower dose versus control second, with the second test considered exploratory (failed) if the first test fails.

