Statistical Methods:	
Sample Size A total of 25 evaluable patients per arm will provide 71.8% power for each test comparing a dose with control via a Fisher's exact test at 1-sided alpha = 0.15 to detect a difference between a control proportion 0.55 and an experimental dose proportion 0.80; these tests will be conducted in a fixed sequence: higher dose versus control first and lower dose versus control second, with the second test considered exploratory (failed) if the first test fails.
 
Analysis populations The following populations will be considered for data summaries. Intent-To-Treat (ITT): All randomized patients. Patients will be analyzed according to the treatment to which they are randomized. The ITT Population will be the primary analysis set for the efficacy variables.
 
Per Protocol (PP): Supporting analyses will be conducted on the PP Population, comprising all patients randomized and treated without major protocol violations during the trial. This population will be documented before final database lock.
 
Safety: All patients who received at least one dose of study treatment. Patients will be included in the analyses according to the treatment they received. The Safety Population will be used in the analyses of all safety endpoints.
 
Primary analysis The primary efficacy analyses will be based on the ITT Population. Fisher exact test will be used to compare the proportion of CRs between each dose and control.
 
Secondary analysis The primary analysis will be repeated using the PP Population as a supportive analysis. Complete response rates and confidence intervals will also be reported for key subgroups (e.g., randomization strata). Analyses of EFS, LFS, time to neutrophil recovery, time to platelet recovery, and OS will be descriptive. Kaplan-Meier (KM) estimates will be used to estimate the survival distribution for each arm and KM plots will be produced to accompany these analyses. Confidence intervals will be reported for medians and KM estimates. Duration of response will be analyzed using a similar approach; the analysis will account for the competing risk of death and the survival distributions will be estimated as cumulative incidence functions.
 
Mortality rate at Day 30, Day 60, and Day 90 will be reported using descriptive statistics in a manner similar to the reporting of the morphologic CR rate. The time to neutrophil and platelet recoveries will be reported using the following descriptive statistics: N, mean, standard deviation, median, minimum, maximum, and 1st and 3rd quartiles.

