6. INVESTIGATION PLAN

6.1 Overall Study Design and Plan Description

This is an exploratory phase II, open-label, randomized, multicenter, parallel group trial to determine whether there is evidence that the addition of either or both different dose levels of CX-01 to standard induction therapy (idarubicin + cytarabine) and consolidation therapy has an additive therapeutic effect in newly diagnosed AML patients when compared to patients receiving standard induction chemotherapy alone.

Approximately 75 patients will be randomized in a 1:1:1 ratio to one of the following treatment groups:

- **Group 1:** Idarubicin + Cytarabine, OR
- **Group 2:** Idarubicin + Cytarabine plus lower dose CX-01 (0.125 mg/kg/hour), OR
- **Group 3:** Idarubicin + Cytarabine plus higher dose CX-01 (0.25 mg/kg/hour)

Eligible patients who meet the inclusion criteria and do not meet any of the exclusion criteria and have provided informed consent will be enrolled in the study. Each patient will participate in the study for approximately 18 months from the time of informed consent through final study contact, or until they withdraw from the study or the study is terminated by the Sponsor.

[figure not shown]
Overall survival data will be collected every 3 months until death or until the end of study by the investigational sites. The end of study will occur approximately 18 months after the last patient is randomized.

A Data and Safety Monitoring Committee (DSMC) will meet periodically to review the safety of the study (see Section 6.6.5). Details describing the DSMC process and procedures will be outlined in a separate DSMC Charter.

Adverse events (AEs) will be collected from time of informed consent and continue until 30 days after the last study treatment is administered. Longer follow-up and collection of AEs may be required for patients that do not have an absolute neutrophil count (ANC) recovery within 42 days (i.e., until the recovery or the reason for no recovery is diagnosed) after the last induction or consolidation cycle.

A flow diagram of the study design is shown in Figure 6—1.

Figure 6—1 Study Design

Abbreviations: AML=acute myeloid leukemia

Note: It is expected that approximately 90 patients will be screened to identify 75 patients for randomization.

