6.4.3 Method of Assigning Patients to CX-01

6.4.3.1 *Patient Identification*

Each newly enrolled patient will be assigned a unique patient identification number using an Interactive Web/Voice Response System (IxRS). Patients will be randomized across all sites. Patients who discontinue from the study will not be replaced.

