6.2 Handling of Dropouts or Missing Data (where applicable)

For ITT analysis, patients with partial or missing data to determine morphologic complete remission on the eCRF form will be considered as not having met the criteria morphologic complete remission. For PP analysis and elsewhere, only the complete cases will be analyzed and no missing value imputation will be carried out.

Incomplete AE-related dates will be handled as follows:

- In cases where:
 - o the onset date is completely missing or
 - o the onset is in the same year (only the onset year is available) as the start of study treatment or
 - o the onset is in the same month and year (only the day is missing) as the start of study treatment or
 - o either the onset day or month is missing but the year is not before start of study treatment then the onset date will be replaced by the minimum of start of study treatment and AE resolution date.
- In all other cases the missing onset day or onset month will be replaced by first day or January.

Statistical Analysis Plan

Version: Final

Date of Issue: 20 March 2018

Cantcx Pharmaceuticals, Inc. Protocol No. CNTX-CX-01 2015 AML I Covance Study ID: 000000146201

- Incomplete stopping dates will be replaced by the last day of the month (if the day is missing only), unless this will result in a date after the date of death. If the imputed date will exceed the date of death, the date of death will be used as the stopping date. No imputation is needed if the event is ongoing.
- In all other cases the incomplete stopping date will not be imputed.

To impute missing day of follow-up dates (such as safety long term follow up) or Disease History, the missing day will be taken as the 15th of the month, as long as month and year is available. In all other cases missing or incomplete dates will not be imputed.

In patient listings, the documented date from cCRF will be reported (e.g. .May2016 in case where the day is missing, but month and year are available).

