7.6 Efficacy

7.6.1 Primary Efficacy Analysis

Fisher exact test will be used to compare the proportion of CRs between each dose and control for the ITT population using one sided test at 15% level of significance along with a 70% CI. These tests will be conducted in a fixed sequence: higher dose versus control first and lower dose versus control second, with the second test considered exploratory (failed) if the first test fails.

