7.6.3 Sensitivity Analysis

None.

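### The 71.8% power assumes 25 evaluable patients per arm, but about 25 per arm are randomized and missing responses count as non-CR, so the basis of the planning rates must be declared and a missing-response check added

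*Protocol*

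**What the plan says.** The sample-size paragraph appears in the synopsis, in Protocol 6.8.1 and in SAP 2.6. It says that "A total of 25 evaluable patients per arm will provide 71.8% power for each test", for "a control proportion 0.55 and an experimental dose proportion 0.80", by a one-sided Fisher's exact test at 0.15. None of these places defines *evaluable*, and the term matches none of the ITT, mITT, PP or Safety sets.

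Protocol 6.1 sets the number: "Approximately 75 patients will be randomized in a 1:1:1 ratio to one of the following treatment groups". The only allowance stated is for screening, 90 screened to give 75 randomized. Protocol 6.4.3.1 adds: "Patients who discontinue from the study will not be replaced". Protocol 6.3.3 says the same.

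The primary test uses the ITT population, meaning all randomized patients (Protocol 6.8.2 and 6.8.8.1; SAP 5 and 7.6.1). SAP 7.6.1 runs it "using one sided test at 15% level of significance along with a 70% CI". For missing data in that analysis, SAP 6.2 says that "patients with partial or missing data to determine morphologic complete remission on the eCRF form will be considered as not having met the criteria". Under the heading "7.6.3 Sensitivity Analysis", the SAP has one word: None.

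Two repeats of the primary endpoint are planned. One is on the PP set (SAP 7.6.2), with complete cases only (SAP 6.2). The other is on the mITT set of randomized and dosed patients (SAP 5; Table 14.2.2 in the shells).

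**The concern.** The power statement counts evaluable patients and the primary test counts randomized ones. With 75 / 3 = 25 randomized per arm, the two numbers agree only if nobody is lost. The documents themselves expect some unassessed patients. SAP 7.2 tabulates those who are randomized but never treated. Protocol Appendix A has an Indeterminate class for death before the first response assessment. The bone-marrow response shell (Table 14.3.2.2.1) lists Indeterminate and Unknown.

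Two things are at stake. The first is whether the sponsor has about 72% power or something lower. The second is whether a positive result could come partly from missing control responses. The trial is open-label, so losses may differ between arms. Counting a missing response as failure works against CX-01 when the loss is in a CX-01 arm, but in its favour when the loss is in the control arm.

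**Working it through.** **Inputs.** Control CR 0.55, CX-01 CR 0.80, one-sided 0.15 and 25 per arm come from Protocol 6.8.1; the 25 randomized per arm follow from Protocol 6.1. The documents give no rate of non-evaluable patients, so losses of 0 to 5 per arm are an assumption.

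**Formula.** Let x and y be the CR counts in control and CX-01. The Fisher p-value is p(x, y) = P(H ≥ y), where H is hypergeometric with 50 patients, x + y responders and 25 drawn. Power is the sum of b(x; 25, pC) × b(y; 25, pT) over all tables with p(x, y) ≤ 0.15, where b is the binomial probability.

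**The plan's own figure.** With pC = 0.55 and pT = 0.80 the sum is 71.7%, against 71.8% stated. The figure reproduces.

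**Equal losses scored as non-CR.** This assumes that 0.55 and 0.80 are rates among evaluable patients. Two loss models were used:

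- Model A multiplies both rates by (1 − k/25). For k = 2 the rates are 0.55 × 0.92 = 0.506 and 0.80 × 0.92 = 0.736.
- Model B fixes k non-responders per arm and draws the rest from 25 − k patients, with the test still on 25 per arm.

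| Non-evaluable per arm | Power, A | Power, B |
|---|---|---|
| 0 | 71.7% | 71.7% |
| 1 | 68.2% | 68.9% |
| 2 | 65.0% | 66.2% |
| 3 | 62.0% | 63.4% |
| 5 | 56.1% | 57.3% |

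If 0.55 and 0.80 already count unassessed patients as failures, pC and pT are unchanged and power stays at 71.7%.

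**False-positive rate.** True CR is set to 0.55 in both arms, with losses in control only:

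| Control losses | Rate, A | Rate, B |
|---|---|---|
| 0 | 10.0% | 10.0% |
| 1 | 13.1% | 12.8% |
| 2 | 16.8% | 16.2% |
| 3 | 21.0% | 20.2% |

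With equal losses of one to three per arm the rate is 10.1% under A and below 10% under B. When both arms lose patients, it is the excess in control that matters. Under B, control/CX-01 losses of 2/1 give 12.3%, 3/2 give 11.8% and 3/1 give 15.7%. Losses in the CX-01 arm alone do not raise the rate. They lower power, to 62.5% with one and 52.4% with two (B).

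**The case against.** The strongest reply is that nothing is miscalculated: 71.8% is correct for its stated premise. That stands. A reader might infer that the power is simply overstated, but the documents do not support that without a condition. The one background rate, in Protocol 6.2, is remission in about 50% to 75% of patients, not of evaluable patients, and the analysis set is everyone randomized. The all-randomized reading is at least as plausible, and under it no power is lost.

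A reader might also infer that the 15% error rate fails whenever losses are unequal. It does not. The exact test is conservative, with an actual rate of 10.0% at CR 0.55, and this absorbs one excess control loss. No document predicts heavier losses in control. The CX-01-specific stopping rules in Protocol 6.4.4.2 (aPTT, and interruption beyond 72 hours) act only in the CX-01 arms. Any missing responses they caused would count against CX-01.

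Finally, it would be wrong to read SAP 7.6.3 as meaning that the primary endpoint is analysed only once. The PP and mITT repeats exist, and the mITT set removes undosed patients, an obvious kind of loss in an open-label trial. But PP also drops patients for protocol deviations and analyses by treatment received, while mITT is defined by dosing alone. Neither asks whether a success would survive if the missing control responses had been remissions.

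**Conclusion.** The mismatch is real and should be corrected, but its effect is conditional. The evaluable size is met only with zero losses. If the planning rates describe evaluable patients, ITT power is about 68-69% with one non-evaluable patient per arm, 65-66% with two, 62-63% with three and 56-57% with five. If they describe all randomized patients, power stands and only a word is wrong. The documents do not settle this.

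Scoring missing as failure is not conservative when control loses more patients. At a true CR rate of 0.55 the false-positive rate is about 13% with one excess control loss, 16-17% with two and 20-21% with three, so it passes 15% only from about two. That threshold is for CR 0.55 and would shift at other rates. The loss counts are assumptions throughout. For a self-described exploratory phase II trial this is a correction worth making, not a flaw that undermines the design.

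**What to change.** 1. In the synopsis, Protocol 6.8.1 and SAP 2.6, declare whether 0.55 and 0.80 are rates among all randomized or among evaluable patients. If all randomized, replace *evaluable* by *randomized* and keep 71.8%. If evaluable, define the term and state ITT power as about 65-66% with two and 62-63% with three non-evaluable patients per arm. The two readings should not be mixed in one sentence.

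2. In SAP 7.6.3, replace the entry None by a tipping-point check on Table 14.2.1. Report the number of missing responses by arm. If the primary test succeeds, report how many missing control responses would have to be CR for it to fail. The count is enough. A re-run that takes the worst case in both arms is not needed: if CX-01 truly reaches 0.80, it would succeed only 57%, 41% and 25% of the time with one, two and three missing per arm.

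The cost is wording, a possibly less favourable stated power, and one small table. No more patients are needed.

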5.1 Primary Objectives

The primary objectives are:

- To assess whether CX-01, administered at any or all studied dose levels in conjunction with standard induction therapy for AML increases the morphologic CR rate based on International Working Group (IWG) criteria
- To assess the safety and tolerability of CX-01, administered at two studied dose levels in conjunction with standard induction therapy for AML.

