2.6 Sample Size and Power

A total of 25 evaluable patients per arm will provide 71.8% power for each test comparing a dose with control via a Fisher's exact test at I-sided alpha = 0.15 to detect a difference between a control proportion 0.55 and an experimental dose proportion 0.80; these tests will be conducted in a fixed sequence: higher dose versus control first and lower dose versus control second, with the second test considered exploratory (failed) if the first test fails.

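### The stated 71.8% power for each test ignores the fixed sequence; formal power for the lower dose is about 59% if both true CR rates are 0.80

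*Protocol*

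**What the plan says.** Protocol 6.8.1 states that "25 evaluable patients per arm will provide 71.8% power for each test comparing a dose with control", and that this is the power "to detect a difference between a control proportion 0.55 and an experimental dose proportion 0.80". The test is given in the synopsis as "Fisher's exact test at 1-sided alpha = 0.15". The synopsis and SAP 2.6 carry the same power statement.

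The sentence that gives the power also gives the testing rule. In SAP 2.6 it ends "with the second test considered exploratory (failed) if the first test fails". SAP 7.6.1 makes this the working rule for the primary analysis: "higher dose versus control first and lower dose versus control second, with the second test considered exploratory (failed) if the first test fails".

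The lower dose is part of the primary question. Protocol 5.1 asks about CX-01 "administered at any or all studied dose levels in conjunction with standard induction therapy for AML", and Protocol 6.1 describes a trial looking for evidence on "the addition of either or both different dose levels of CX-01".

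Neither document gives a power for the lower-dose test under the sequence, a probability that both tests succeed, or a statement of what is assumed for the two doses jointly. The rate of 0.80 is given only for a single, unspecified experimental dose.

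**The concern.** A power figure attached to each test should be the chance that the test succeeds as the plan defines success. For the lower dose the plan defines success more narrowly than the calculation does: even if the lower dose beats control on its own Fisher test, the result is counted as failed when the higher dose has missed. The power of that second test is therefore the probability that both tests reject, which is smaller than the power of either one alone.

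The reader cannot recover the smaller figure from 71.8%. It depends on the correlation induced by the shared control arm and on the true higher-dose rate, which the plan does not specify alongside a lower-dose claim. One third of the patients go to the lower-dose arm, so anyone judging what that arm can deliver formally would start from a figure that is too high.

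**Working it through.** **Inputs.** 25 evaluable patients per arm, control CR rate 0.55, experimental rate 0.80, one-sided Fisher test at 0.15 (Protocol 6.8.1 and synopsis); 1:1:1 allocation with one control arm (Protocol 6.1); higher dose tested first, lower dose second and counted as failed if the first fails (Protocol 6.8.1, SAP 7.6.1). One assumption is added: for the headline figure, 0.80 is applied to both doses, because it is the only experimental rate the plan gives.

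**Step 1: reproduce the stated figure.** With c responders of 25 on control and t of 25 on a dose, the one-sided Fisher p-value is P(X ≥ t), where X is hypergeometric (50 patients, c + t responders, 25 drawn). Reject if p ≤ 0.15. Let g(c) be the probability, over t ~ Bin(25, 0.80), of rejecting given c. Then

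marginal power = Σ P(c) g(c), with c ~ Bin(25, 0.55), = 0.7171.

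This agrees with the stated 71.8% to 0.1 point. The stated figure is therefore the ungated power of a single comparison.

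**Step 2: apply the sequence.** Given c, the two dose arms are independent, so

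P(both reject) = Σ P(c) g_H(c) g_L(c) = 0.5869 with both doses at 0.80.

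A simulation of 2,000,000 trials gave 0.5867. Multiplying the two powers as if the tests were independent would give 0.7171² = 0.5142; the shared control raises the true value to 0.5869.

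**Step 3: all outcomes, both doses at 0.80.**

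| Outcome | Calculation | Probability |
|---|---|---|
| Both reject (formal success for both doses) | Step 2 | 58.7% |
| Higher dose only | 0.7171 − 0.5869 | 13.0% |
| Lower dose passes its own test but is counted as failed | 0.7171 − 0.5869 | 13.0% |
| Neither | 1 − (0.5869 + 0.1302 + 0.1302) | 15.3% |

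**Step 4: vary the true higher-dose rate, lower dose held at 0.80.**

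| True higher-dose CR rate | Formal power, higher dose | Formal power, lower dose |
|---|---|---|
| 0.55 | 10.0% | 9.6% |
| 0.65 | 28.2% | 26.0% |
| 0.75 | 56.6% | 48.6% |
| 0.80 | 71.7% | 58.7% |
| 0.85 | 84.9% | 66.0% |
| 0.90 | 94.2% | 70.1% |
| 1.00 | – | 71.7% |

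The lower-dose figure reaches its marginal value only as the higher-dose rate approaches 1.00.

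**The case against.** The best defence is that the sentence is literally true and qualifies itself. It describes power for a test comparing a dose with control, which is per-comparison power, and then discloses the gate in the same sentence. Quoting marginal power and stating the sequence separately is common practice. This stands in part: there is no arithmetic error and nothing is hidden. But disclosing the rule does not disclose what it costs, and the figure is offered for each test without being labelled marginal.

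A second point is that if the higher-dose test has already passed, the lower-dose test rejects with probability 0.5869 / 0.7171 = 81.8%, which is above 71.8%. That is correct, but it is conditional on a result not known at planning. It is not the chance at the outset that the lower dose succeeds.

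Third, the 59% rests on a joint assumption the plan does not make. That is fair, and it is why the range belongs beside the figure. The direction does not depend on the assumption: at every higher-dose rate in the table below 1.00, gated power is under the marginal 71.7%.

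Fourth, 71.7% is also the chance of formal success for at least one dose, but only when the true higher-dose rate is 0.80. If the higher dose is at 0.55, the chance of any formal success is 10.0%, however active the lower dose is. This limits what 71.8% can be said to show about the either-dose question.

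Finally, this is an exploratory phase II trial, and the primary outcome table shell reports a difference, interval and p-value for both doses. That limits the consequences, but it does not make the planning figure right for the second test.

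**Conclusion.** The concern holds. The figure of 71.8% is correct as marginal power and is the formal power of the higher-dose test. It is not the formal power of the lower-dose test under the plan's own rule, which is 58.7% if the control rate is 0.55, both dose rates are 0.80 and all 25 patients per arm are evaluable. The overstatement is 13.0 points against the exact marginal value, and larger if the higher dose is less active than 0.80.

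This is a labelling and completeness fault in the planning statement. The fixed sequence is a sound decision rule and is openly described. The statement should be corrected, but the validity of the design and analysis is not in question.

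**What to change.** Amend the sample-size statement in three places: the protocol synopsis, Protocol 6.8.1 and SAP 2.6.

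- Label 71.8% as the marginal power for each comparison taken alone, which is the formal power for the higher dose only.
- Add a clause such as: *about 59% power for the lower dose versus control under the fixed sequence if both true CR rates are 0.80 (49% if the higher-dose rate is 0.75, 66% if it is 0.85).*

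Fisher's test, the testing order, the one-sided 0.15 level and the sample size do not change. The cost is one label and one clause in each place, and a less favourable stated figure for the lower dose.
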